5.2 Method for Assigning Subjects to Treatment Groups

This is a cluster randomized controlled design. A computer generated randomization sequence will assign schools to simple or complex treatment.

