6.4 Control/Comparison Group and Confounding Factors

Complex prevention is the "comparison" while simple prevention is the "intervention" group. Both groups receive primary and secondary prevention and we expect both protocols to be similarly effective in reducing untreated caries.

We will include relevant confounders a priori in our analysis, including: gender, previous (or concurrent) dental treatment (identified as new or existing treated dentition at examination), age at examination, race/ethnicity, and any school-level indicators. As these data have a multilevel structure, we will additionally assess caries incidence and prevalence using multilevel mixed effects Poisson and logistic modeling (ML-MEM). We will examine the effects of comprehensive prevention at multiple levels (tooth, child, grade, and school). In this analysis, we will be able to explore the variation in clinical outcomes across child and school levels. For all GEE and multilevel models, we will conduct analysis for outcomes (caries prevalence and incidence) measured by all teeth, all adult teeth only, and all deciduous teeth only.

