7.1 Sample Size Determination

The study is powered to the primary outcomes of caries arrest and caries prevention between twice-yearly simple and complex prevention. We expect to enroll approximately 14,100 students across the initial 60 schools over the duration of the study (N=235 per cluster). The remaining 16 schools will contribute approximately 3760 participants. From our pilot studies of school-based caries prevention, baseline caries prevalence is approximately 40%. Our power estimates assume an equal proportion of success, π , of 20% caries arrest. With a given non-inferiority margin (δ) of 10%, a total sample size per group of 198 (N_{tot} = 396) is required for an alpha of 5% and a power of 80%²⁹. However, as we use a cluster randomized design, this sample size is inflated to account for clustering (intraclass correlation coefficient = .10) by a design effect of 24.4 to a total required sample of 9,662.

For caries prevention, both interim therapeutic restorations and silver diamine fluoride have been shown to be 80% efficacious in individual clinical trials. Power for the repeated measures design was estimated using the method of Diggle et al (2002) for generalized estimating equations ³⁰. For power estimates, we control for the baseline prevalence of untreated decay. We assume a conservative average number of visits per child of 6, with a power of .80 and an alpha of 5%. We further assume a repeated measures correlation of 0.5 and a per-visit attrition rate of 20%. For a given minimally detectable effect size (standardized effect size difference) of .25, an attrition and clustering adjusted sample size of 12,874 is required. Thus, our study is powered for these conservative assumptions for caries prevention. Further, we note that in the presence of the nonlinear link function, ME-GLM is more powerful than GEE, thus our power estimates are conservative and the anticipated sample size is sufficient for analysis.

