7.2 Statistical Methods

For caries arrest, we will first determine the per-patient proportion of carious lesions treated with simple versus complex prevention that stayed arrested throughout the length of the study. The percentage of arrested caries (at the child level) will be modeled using multilevel binomial regression. Our noninferiority margin, δ , is set at 10%. Our null hypothesis is that simple prevention is not inferior to the complex prevention by at least δ : π_{simple} - $\pi_{\text{complex}} \ge \delta$. Our alternative hypothesis is that π_{simple} - $\pi_{\text{complex}} < \delta$. We will use differences in effect sizes as estimated by confidence intervals to determine clinical non-inferiority of the two prevention methods. For the prevention of new caries, we will use generalized estimating equations (GEE) with a logit link (caries prevalence) and a negative binomial link (caries incidence), assuming an exchangeable correlation matrix, to evaluate longitudinal effects of comprehensive care untreated decay. We will identify the number of teeth at risk for each child during each follow-up interval and determine the number of those teeth in which new caries is observed at the examination that ends that interval. Primary teeth lost in each interval and new permanent teeth will not contribute to data for that interval. To explore non-linear trends in untreated decay between simple and complex prevention, we will use generalized additive models (GAMs) with non-parametric smoothers. Longitudinal effects of simple and complex prevention on academic outcomes, compared to untreated children, will be analyzed using propensity score-matching and multilevel modeling. First, we will estimate propensity scores for each participant at baseline, establishing the probability of treatment assignment conditional on observed covariates (e.g., prior academic performance). Propensity scores will be used to match treatment students to students not receiving treatment, considering multiple forms of matching
such as nearest neighbor and caliper. Treated students and matched comparators will then be analyzed using multilevel mixed effects linear regression (for academic achievement) and Poisson regression (for school absences).

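### The GEEs for caries prevention, a primary outcome of a school-randomised trial, state neither cluster unit nor variance estimator, and the documents point to the child as the cluster

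*Combined protocol and SAP*

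**What the plan says.** Allocation is by school (Section 5.2): "A computer generated randomization sequence will assign schools to simple or complex treatment". The Study Summary and Section 7.1 both list caries prevention among the primary outcomes.

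For prevention, Section 7.2 plans GEEs with a logit link for prevalence and "a negative binomial link (caries incidence), assuming an exchangeable correlation matrix, to evaluate longitudinal effects". It names no cluster unit and no variance estimator. The same section uses a multilevel binomial model for caries arrest, and says that confidence intervals will be used to judge non-inferiority of the two methods.

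In Section 7.1 the power calculation for this GEE is described as a repeated-measures design with six visits per child: "We further assume a repeated measures correlation of 0.5 and a per-visit attrition rate of 20" per cent. The resulting 12,874 is said to be adjusted for attrition and clustering. The school-level ICC appears only in the arrest paragraph: "as we use a cluster randomized design, this sample size is inflated to account for clustering".

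Section 6.4 adds: "As these data have a multilevel structure, we will additionally assess caries incidence and prevalence using multilevel mixed effects Poisson and logistic modeling". It mentions effects at tooth, child, grade and school level and lists school-level indicators among the covariates. No section says whether the GEE or the mixed model decides non-inferiority for prevention.

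**The concern.** A standard GEE has one level of clustering, and its robust variance protects only against correlation inside the clusters it is given. With the child as cluster, visits within a child are covered but children in the same school are treated as independent. As whole schools are allocated, the school-to-school variation that remains in each arm then drops out of the standard error.

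Four features point to the child:

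- The only correlation attached to this GEE is the 0.5 between repeated measures.
- The GEE is introduced for longitudinal effects, with data organised by child and follow-up interval.
- Section 7.2 says multilevel for arrest and for the academic outcomes, but not for prevention.
- Section 6.4 assigns the multilevel structure to models that come in addition.

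Inflating the sample size does not repair this, because the analysis has to carry the school variance as well. School-level covariates remove only the part of it that they explain. Intervals that are too narrow make it too easy to call a truly worse programme non-inferior. At the least, two analysts following Section 7.2 could report standard errors that differ several-fold on a primary outcome.

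**Working it through.** **Inputs from Section 7.1.** "We expect to enroll approximately 14,100 students across the initial 60 schools over the duration of the study (N=235 per cluster"), so 30 schools per arm and 235 children per school; "intraclass correlation coefficient = .10" (arrest paragraph); six visits and a repeated-measures correlation of 0.5 (prevention paragraph).

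**The plan's own figures (arrest).**
- Sample size per group = (1.645 + 0.842)² × 2 × 0.20 × 0.80 / 0.10² = 198, or 396 in total. This matches the plan and implies a one-sided 5% level; a one-sided 2.5% level gives 252.
- Design effect = 1 + (235 − 1) × 0.10 = 24.4, and 396 × 24.4 = 9,662. The plan reads "by a design effect of 24.4 to a total required sample of 9,662". Both reproduce.

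**The prevention figure.** The usual repeated-measures formula with standardised effect 0.25 gives, two-sided, 2 × (1.96 + 0.842)² × (1 + 5 × 0.5) / (6 × 0.25²) = 147 per arm, or 294 in total. Then 294 × 24.4 = 7,174 before attrition. Neither the attrition method nor the ICC for prevention is stated, so 12,874 cannot be recovered uniquely.

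**Consequence if the GEE is clustered on child only.** Take a linear outcome with total variance 1: school 0.10, child within school 0.40 (so that visits correlate 0.5), residual 0.50. Assume no attrition and a school effect that is constant across visits.

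Six visits, variance of one arm mean:
- With schools: 0.10/30 + 0.40/(30 × 235) + 0.50/(30 × 235 × 6) = 0.003333 + 0.0000567 + 0.0000118 = 0.003402
- Children treated as independent: (0.5 + 0.5/6)/(30 × 235) = 0.0000827
- Ratio 41.1; standard-error factor √41.1 = 6.4
- Coverage of a nominal 95% interval: 2Φ(1.96/6.41) − 1 = 0.24

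One visit: the ratio is the design effect 24.4, the factor is √24.4 = 4.94, and coverage is 2Φ(1.96/4.94) − 1 = 0.31.

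The same formulas with other ICCs, which are assumptions:

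| School ICC | Visits | SE factor | Coverage of 95% CI |
|---|---|---|---|
| 0.01 | 1 | 1.83 | 72% |
| 0.01 | 6 | 2.24 | 62% |
| 0.05 | 1 | 3.56 | 42% |
| 0.05 | 6 | 4.59 | 33% |
| 0.10 | 1 | 4.94 | 31% |
| 0.10 | 6 | 6.41 | 24% |

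A simulation of the six-visit case at ICC 0.10 (2,000 runs) gave a two-sided error of 0.75 with the child as cluster, against 0.76 by formula, and 0.05 with the school as cluster.

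**The case against.** The strongest reply is that the plan is silent, not wrong. No sentence makes the child the cluster. The 0.5 is a power input, not an analysis specification. An exchangeable GEE can be clustered on school, and its robust variance is then valid even though one correlation cannot describe both visits within a child and children within a school. That stands: a reader might infer that the planned intervals certainly leave out the school variance, and the documents do not establish this.

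A second reply is that a school-level analysis of prevention is already planned. Section 6.4 has mixed models for the same outcomes, and Section 7.1 closes its prevention paragraph by comparing a mixed model with GEE. This also stands, but only in part. Those models are described as additional, the Study Summary names GEE in its headline methods, and nothing makes the mixed model decisive.

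Third, the size is conditional. The ICC of 0.10 is borrowed from arrest. The calculation is linear although the planned models are logit and negative binomial, and it ignores the 20% attrition per visit and the planned school-level covariates. All of this is correct, and it is why the lower ICCs and the one-visit case are shown. The factor stays above 1.8 in every case in the table.

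**Conclusion.** The prevention GEEs lack a stated cluster unit and variance estimator, the deciding model is not named, and the text leans towards the child as cluster. If that is what is run, standard errors are too small by about 4.9 to 6.4 times at ICC 0.10 with 235 children per school, and by about 1.8 to 4.6 times at assumed ICCs of 0.01 to 0.05. This goes beyond missing detail, because a primary conclusion rests on the intervals.

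Three stronger statements go too far:

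- A reader might infer that school is the largest variance component. In the decomposition above it is the smallest (0.10 against 0.40 and 0.50). It dominates only the variance of the arm contrast, about 98% in the six-visit case (0.003333/0.003402), because it is divided by 30 schools and not by 7,050 children.
- A reader might attach a false non-inferiority rate to prevention. The 10% margin stands in the arrest text as a difference in proportions, and no margin is given on either GEE scale.
- A reader might extend the point to the once- versus twice-yearly comparison. Section 7.2 specifies no GEE for it.

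**What to change.** In Section 7.2, do one of the following and state that it decides non-inferiority for prevention:

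1. Name school as the clustering unit for the robust variance of both prevention GEEs, prevalence and incidence. With 60 schools a small-sample correction (for example Kauermann-Carroll or Mancl-DeRouen, with a t reference) is a sensible option.
2. Make the Section 6.4 multilevel model the deciding analysis, with random effects for school and for child written out, and keep the GEE as supportive.

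The first keeps the planned population-averaged effect. The second changes the target to a conditional effect on the logit scale, which the text should say.

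The cost is a sentence in the plan and an option in the code, with no new data. Intervals will be wider than under child clustering, which the clustering-adjusted sample size in Section 7.1 already assumes.

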For the purposes of the analysis on dental-related service use and costs among Medicaid beneficiaries, all children participating in Medicaid of elementary school age will be included in the analysis, except for children in participating schools that do not provide informed consent to provide oral health and Medicaid dental service use data.

The Primary Specific Aims are to:

- 1. Determine the non-inferiority of simple vs complex caries prevention for preventing new caries (primary prevention).
- 2. Determine the non-inferiority of simple vs complex caries prevention for arresting current caries (secondary prevention).
- 3. Determine the impact of simple vs complex prevention on child oral healthrelated quality of life
- 4. Determine the impact of once per year vs twice per year care on the arrest and prevention of caries

Notably, toothaches or office based dental care reduces in-class learning time. If the caries prevention programs are as effective as predicted, knowing the time/trade-off will be important. Thus a secondary outcome of the study will be school performance (school absence and student achievement). To insure accurate assessments, program participants will be compared to children in their own schools and to children in NYC "peer schools" not participating in the study. No additional data is collected for educational outcomes from participants.

The Secondary Specific Aims are to:

- 1. Determine the impact of prevention vs no prevention on school absence
- 2. Determine the impact of prevention vs no prevention on standardized test performance
- 3. Determine the impact of simple vs complex prevention on school absence and test performance

The exclusion criteria will be those: (1) not attending participating schools, (2) those attending participating schools without informed consent, or (3) those attending participating schools with informed consent, but without assent and (4) those allergic to silver.

For the purposes of the analysis on dental-related service use and costs among Medicaid beneficiaries, the only excluded groups are (1) children not participating in Medicaid will be excluded and (2) children participating in Medicaid in Caried*Away* schools, but without informed consent to provide oral health and Medicaid dental service use data.

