The inclusion criteria for the schools enrolled in groups (1) and (2) include: A Hispanic/Latino population of at least 50% and a free and reduced lunch population of at least 80%. The remaining racial/ethnic and socioeconomic of the schools beyond these criteria can include children from any race/ethnicity and economic background. The inclusion criteria for schools in group (3) include any elementary school in New York City. Schools in group (3) will be balanced to ensure representation from every primary race/ethnic group and from all socioeconomic tertiles.

The impact of COVID-19 has greatly impacted our in school-based cavity prevention approach. Elementary schools have closed, delayed in opening and will either allow students to return to schools part-time under a blended learning model or will learn at home remotely full-time. This has impacted our ability to provide preventive services in some or possibly all of our schools. In order to continue to provide these services, our community engagement administrator will reach out to those schools where we cannot currently provide in school care, seek their guidance in helping to identify and connect with local community-based organizations in their area and then telephone these local organizations to discuss participation in the research study.

Once an alternate community-based location has been identified and is interested in participating, our HCP will meet with the community organization staff to review COVID-19 safety precautions at the community-based location, clinical protocols, room size and safe distancing requirements. NYUCD HCP will fill out the Caried*Away* COVID-19 community-based location does not meet the requirements listed in the checklist, the NYUCD HCP will notify the Principal Investigator that the site is not an acceptable location for providing safe care.

If the community-based location meets the requirements of the Caried*Away COVID-19* community-based checklist and wishes to participate, the NYUCD HCP will review the Memorandum of Understanding (MOU). As community organizations are identified and sign an MOU we will submit their name and location to the IRB.

All clinical personnel will wear personal protective equipment consistent with CDC, DOH, FDA and NYU Dentistry guidelines.

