Care will be provided by NYUCD licensed dentists, dental hygienists, nurses, and/or advanced level dental hygiene students supervised by licensed dental professionals to all participating students at all locations. After the child has completed treatment they will be required to put their mask back on and apply an alcohol-based hand sanitizer. The dental assistant will bring the child to the waiting room area. The child will be escorted back to the classroom by the school's parent coordinator or back home by the parent/guardian from the community-based, or NYUCD locations.

Simple prevention takes approximately 5 minutes and is aerosol free. It consists or a gentle tooth brush cleaning, oral hygiene instruction, an examination, delivery of silver diamine fluoride which takes approximately 1 minute to apply using Advantage Arrest Applicators to all pits and fissures on bicuspids or molar teeth, and to all posterior, asymptomatic carious lesions. Fluoride varnish is then applied which also takes 1 minute to apply.

Complex prevention takes approximately 20 minutes and is aerosol. It consists or a gentle toothbrush cleaning, oral hygiene instruction, an examination, delivery of glass ionomer sealants to all pits and fissures on bicuspids or molar teeth, and to all asymptomatic carious lesions. This takes about 5 minutes to provide care to ¼ of the mouth at a time. Fluoride varnish is then applied which takes approximately 1 minute.

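### Section 7.2 counts caries incidence per follow-up interval with no exposure-time term, so the once- versus twice-yearly comparison would show a ratio near 2 when the true rates are equal

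*Combined protocol and SAP*

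**What the plan says.** Section 7.2 analyses new caries by generalized estimating equations, with a logit link for prevalence and "a negative binomial link (caries incidence), assuming an exchangeable correlation matrix". The incidence data are then defined tooth by tooth and interval by interval: "We will identify the number of teeth at risk for each child during each follow-up interval", after which the analyst is to "determine the number of those teeth in which new caries is observed at the examination that ends that interval". The only exposure mentioned is the number of teeth.

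Section 6.4 lists the covariates as "gender, previous (or concurrent) dental treatment (identified as new or existing treated dentition at examination), age at examination, race/ethnicity, and any school-level indicators". It also adds multilevel Poisson and logistic models. It names neither an offset nor the time since the previous examination.

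Section 3.2 has caries arrest and prevention assessed at every visit and puts the main prevention time point at 3 years. Sections 1.2 and 3.1 schedule visits twice a year in 60 randomised schools (30 simple, 30 complex) and once a year in 16 selected schools that receive simple care.

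Section 1.2 lists as its fourth primary specific aim: "Determine the impact of once per year vs twice per year care on the arrest and prevention of caries". Section 2.2 treats the same comparison as a secondary objective, and 3.1 as a secondary hypothesis of equal effectiveness.

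**The concern.** A count of newly carious teeth grows with both the number of teeth watched and the length of time they are watched. Section 7.2 allows for the first and says nothing about the second. In the frequency comparison the missing quantity is tied to the group: under the planned schedule every once-yearly interval is about twice as long as every twice-yearly interval. Per interval, the once-yearly group therefore collects roughly double the new caries even if visit frequency makes no difference.

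Section 7.2 offers no separate incidence analysis for this aim, so the aim inherits the per-interval rule. At stake is the conclusion on whether yearly care does as well as twice-yearly care. The rule would count against yearly care when the two are equal, exaggerate a real disadvantage and hide a real advantage.

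**Working it through.** The plan gives no figure of its own on this point, so there is none to reproduce. The check is what the stated counting rule returns when the true rates are equal.

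**Inputs**
- Interval length L: about 0.5 year in the twice-yearly schools and about 1 year in the once-yearly schools (visit schedule in 1.2 and 3.1; examination at each visit in 3.2).
- Rate h of new caries per tooth-year: not given in the documents. Assumed constant, equal in both groups, and varied from 0.02 to 0.20.

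**Formula.** The chance that a sound tooth shows new caries at the examination closing an interval is P(L) = 1 − exp(−hL). The once/twice ratio per interval is [1 − exp(−h)] / [1 − exp(−h/2)], which simplifies to 1 + exp(−h/2). It is therefore close to 2 for any small h.

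| h per tooth-year (assumed) | P, 6 months | P, 12 months | Ratio per interval | Ratio after dividing each by its L |
|---|---|---|---|---|
| 0.02 | 0.00995 | 0.0198 | 1.99 | 1.00 |
| 0.05 | 0.0247 | 0.0488 | 1.98 | 0.99 |
| 0.10 | 0.0488 | 0.0952 | 1.95 | 0.98 |
| 0.20 | 0.0952 | 0.1813 | 1.90 | 0.95 |

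The last column is half the one before it. It falls slightly below 1 because a tooth can become newly carious only once.

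**In a fitted model.** Equal rates were simulated 100 times: 30 twice-yearly and 16 once-yearly schools, 60 children per school, 20 teeth per child, 0.10 per tooth-year, 3 years, with school and child random effects. Apart from the school numbers, the group schedules and the 3 years, these settings are assumptions. The model was negative binomial with a log link and school-clustered standard errors.
- Offset log(teeth at risk): mean once/twice ratio 1.95; equality rejected at the 5% level in 100% of runs.
- Offset log(teeth at risk × interval length): mean ratio 0.97; equality rejected in 6% of runs.

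**Common calendar span.** Over 3 years, six half-year intervals and three one-year intervals give the same cumulative chance, 1 − exp(−3h). At h = 0.05 that is 0.139 in both groups, a ratio of 1.

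**Simple versus complex.** Both arms are planned at L = 0.5, so the ratio is 1.00. Lengthening the intervals equally in both arms leaves it at 1.00. It moves only if mean intervals differ by arm: at h = 0.10, an interval 10% longer in one arm (0.55 against 0.5 year) gives 1.10, and one 25% longer (0.625 against 0.5 year) gives 1.24. These two differences are illustrations; the documents give no interval lengths by arm.

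**The case against.** The best defence is that 7.2 is silent and does not exclude a time term. It writes out no linear predictor at all, and even the use of teeth at risk as an offset is left to be understood. It speaks of incidence, of longitudinal effects and of smooth trends, and each of these implies a time variable. A competent analyst might add the offset as routine. Section 3.2 also sets a common 3-year time point. The comparison affected is secondary and unpowered (7.1 powers twice-yearly simple against twice-yearly complex), and its 16 once-yearly schools are selected, not randomised. Section 7.2 never says that the interval count will be used for it.

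Much of this stands. It limits the point to what would happen if the rule were applied as written, and it lowers the severity. It does not remove the point. Section 7.2 is specific about how to count and against which denominator, and following it literally gives the wrong answer for a listed aim. The 3-year time point is not carried into 7.2 as a cumulative outcome. Age at examination, the nearest covariate in 6.4, does not measure time since the previous examination.

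A reader might go further and infer that pandemic gaps bias the randomised comparison towards a false finding of non-inferiority for simple care. Section 3.1 does report that "Elementary schools have closed, delayed in opening", and 6.3 says "Complex prevention takes approximately 20 minutes and is aerosol", against about 5 aerosol-free minutes for simple care. The documents do not support that inference:
- Nothing shows that gaps differed by arm, and 6.5.1 randomises in sets of two within each yearly wave, so general closures should on average fall on both arms alike.
- A longer visit does not imply wider spacing between visits.
- Section 1.4.2.2 describes the study's care as aerosol-free, which conflicts with 6.3. The two statements need reconciling and cannot support a claim about direction.
- The 10% margin in 7.2 is set out for caries arrest as a difference in proportions; how a margin would apply to an incidence ratio is not stated.

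**Conclusion.** The point holds for caries incidence in the once- versus twice-yearly comparison. With equal, constant rates of 0.02 to 0.20 per tooth-year (assumed) and the planned spacing, the counting rule as written returns a once/twice ratio of 1.90 to 1.99. The size hardly depends on the assumed rate; it does depend on the rate being roughly constant over the year and on no time term being added.

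The randomised simple versus complex contrast has no built-in bias from this source. It would be distorted only if actual intervals turned out to differ by arm, and the documents give no evidence that they do. Nor should the point be extended to the logit prevalence outcome, which is not an interval count.

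This should be fixed before analysis. It falls short of a must-fix because the one distortion that follows from the design lies in a secondary, non-randomised comparison.

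**What to change.** In 7.2:
1. Define caries incidence as new carious teeth per tooth-year at risk.
2. Include log(teeth at risk × years since the previous examination) as the offset in the negative binomial model, and the same offset in the Poisson models of 6.4. Use actual examination dates, so that intervals lengthened by closures are handled by the same term. An ordinary covariate for interval length would not do: under the planned schedule it coincides with the once/twice grouping and cannot be separated from it.
3. Compare once- with twice-yearly care over a common calendar span, for example baseline to the 3-year time point in 3.2. State how teeth lost or newly erupted within that span are counted, since 7.2 drops them interval by interval.

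A binomial model with a complementary log-log link and log interval length as the offset is an alternative; under a constant rate it also removes the small remainder in the last column of the table.

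The cost is analysis wording only, assuming examination dates are held in the electronic record; the documents do not list that field. The change removes the artefact of spacing. It does not make the once-yearly schools, chosen under different criteria, comparable with the randomised ones.

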6.1.6 Examination and Diagnosis

Each program will use password-protected Apple iPads with electronic dental records pre-populated with demographic information of all students with informed consent. Student lists on the Apple iPads will be used to: collect students during the care delivery days; record clinical findings and care delivered; and generate take home forms (see below). On the scheduled care days, we will provide a gentle toothbrush cleaning, oral hygiene instruction, a toothbrush and fluoridated toothpaste. We will also carry out an examination and provide preventive care.

The examination will include a soft tissue inspection and an assessment of all primary and permanent teeth to determine the presence/ absence of decay (active or arrested), missing, filled, or sealed surfaces on all teeth.

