7.3 Subject Population for Analysis

For study outcomes, participants will be analyzed using intent to treat. All participants will be analyzed as randomized in the original randomization, regardless of whether or not they received an intervention.

For dental-related service use and costs, all New York City elementary school-age children enrolled in Medicaid will be analyzed using intent-to-treat.

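### Section 7.2 groups the academic analysis by treatment received, which does not match the 7.3 rule and can tilt the absence comparison toward an apparent benefit

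*Combined protocol and SAP*

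**What the plan says.** Section 7.2 describes the academic analysis as prevention "compared to untreated children, will be analyzed using propensity score-matching and multilevel modeling". The matching step is "Propensity scores will be used to match treatment students to students not receiving treatment", and the outcome model takes the same groups: "Treated students and matched comparators will then be analyzed using multilevel mixed effects linear regression", with Poisson regression for absences. The propensity score is estimated at baseline for each participant, as the probability of treatment assignment. Prior academic performance is the only covariate named, and only as an example.

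Section 7.3 sets intent to treat for study outcomes, with no exception for academic ones: "All participants will be analyzed as randomized in the original randomization, regardless of whether or not they received an intervention".

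The comparator differs by section. In 1.2, "program participants will be compared to children in their own schools and to children in NYC" peer schools outside the study. In 2.2 it is matched students in non-participating schools only. In 7.2 it is untreated children, with no school restriction.

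On delivery of care in school, section 6.1.6 says: "Student lists on the Apple iPads will be used to: collect students during the care delivery days".

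**The concern.** Sections 7.2 and 7.3 classify one kind of child differently: the child whose parent consented but who was never seen. Section 7.3 keeps that child in the program group. Read literally, 7.2 removes the child from it, and where own-school comparators are used (section 1.2) nothing prevents the child from being matched as a control.

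This matters because absence is a secondary outcome, hypothesised in 2.2 to fall with prevention. A child collected in school must be present to receive care. Children with high absence are then under-represented among the treated and, if eligible, over-represented among the controls. Both push the comparison toward benefit when the true effect is nil. Matching on baseline variables does not fully repair this, because the selection acts through absence during follow-up.

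**Working it through.** **Plan's own figure.** The documents give no sample size, effect size or absence rate for the academic analysis, so there is nothing to reproduce. All absence inputs below are assumptions.

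**Set-up.** Let a child's daily absence probability be a, following a Beta distribution with mean m = 6-10% and SD s = 5-8%, over a 180-day year with no true effect. With c independent chances to be seen, a child is treated with probability 1 − a^c. Mean absence among the treated is

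[m − E(a^(c+1))] / [1 − E(a^c)].

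For c = 1, E(a²) = m² + s², so the treated mean is m − s²/(1 − m), and the relative reduction against all consenters is s²/[m(1 − m)].

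**One chance, at the corners of the assumed range:**

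| m | s | s²/[m(1 − m)] | Days: 180 × s²/(1 − m) |
|---|---|---|---|
| 0.06 | 0.05 | 0.0025/0.0564 = 4.4% | 0.48 |
| 0.06 | 0.08 | 0.0064/0.0564 = 11.3% | 1.23 |
| 0.10 | 0.05 | 0.0025/0.0900 = 2.8% | 0.50 |
| 0.10 | 0.08 | 0.0064/0.0900 = 7.1% | 1.28 |

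This gives about 3-11%, or 0.5-1.3 days per 180.

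**Three chances.** The largest value is at m = 0.06, s = 0.08, where E(a³) = 0.002516 and E(a⁴) = 0.000807. The treated mean is (0.06 − 0.000807)/(1 − 0.002516) = 0.0593, a reduction of 1.1% (0.12 days). The smallest is 0.1%, at m = 0.10, s = 0.05.

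**Five chances.** At most 0.2% (0.02 days).

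**Cross-check by simulation under no effect.** One million children, 180 days, at (m, s) = (0.06, 0.05) and (0.10, 0.08). Against all children, as a stand-in for peer schools, treated children show 0.5 to 1.4 fewer days with one care day, 0.1 to 0.4 with two, and about 0 with five. The top figure is slightly above 1.28 because the care day itself counts as a day present. Exact matching on prior-year absence (year-to-year correlation 0.5 or 0.7) leaves 0.3 to 1.1 days with one care day and 0.1 to 0.3 with two.

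**Own-school controls.** Take the 35% consent rate in section 6.6 and assume consent is unrelated to absence. The untreated pool is then 65% non-consenters plus the missed consenters. For m = 0.10, s = 0.08 and one care day, treated children average 18.0 − 1.37 = 16.6 days and missed consenters 16.6 + 13.8 = 30.4. The pool mean is (0.65 × 18.0 + 0.035 × 30.4)/0.685 = 18.6, a false difference of about −2.0 days. For m = 0.06, s = 0.05 it is about −0.8. With two care days the two values are about −0.6 and −0.15, and with five about 0.

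**Under the 7.3 rule.** If every consented child stays in the program group whether seen or not, care-day selection is zero by construction.

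**The case against.** The strongest reply is that treatment in 7.2 means program participation. The propensity score is estimated for each participant and models assignment. Section 6.1.1 makes a child a participant by consent, and 4.1 defines the study population the same way. Section 1.2 compares program participants, and 2.2 draws comparators only from non-participating schools, where no missed consenter would be found. On that reading 7.2 supplies the model, 7.3 the population, and care-day selection does not arise. The reading is available, but 7.2 does not state it: it words the groups by receipt three times, although the Medicaid analysis in the same section defines its contrast by school participation. Section 2.2 also words its exposed group by receipt.

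A second reply is that a child rarely has only one chance. Section 8.24 mentions a treatment week, care recurs over four or five years, 7.1 assumes an average of six visits per child, and from year 3 care is also offered at community sites and the college (6.9), with new dates offered to families who cannot attend (6.1.2). This stands, and it can bring the bias close to zero. Independent chances are themselves favourable, since one illness can span several care days.

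Third, the 7.3 rule is to analyse as randomized. Outside comparators and the 16 once-yearly schools were never randomized, so the mismatch concerns only consented, unseen children. That is correct. So is the point that prior absence, though not named, is not excluded by a covariate list given as an example.

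**Conclusion.** The point holds as a mismatch between 7.2 and 7.3 over how consented but unseen children are classified, with a resulting risk of bias in the absence comparison. The direction, toward benefit, follows if 7.2 is applied as worded. Under the assumed mean (6-10%) and SD (5-8%) of daily absence, the size is about 3-11% (0.5-1.3 days per 180) with one chance to be seen, about 1% or less with three, and near zero over a full treatment week. The documents give neither absence rates nor the number of care days per visit, so they do not settle where in this range the trial falls.

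A reader might infer three stronger things that the documents do not support. One is that the analysis certainly produces a false reduction; it may produce almost none. Another is a very large artefact from using missed consenters as the whole control group: under the same assumptions that contrast would be 22-68%, but no section describes such a group. The third is the larger bias (5-20%) that would follow if treated meant seen at both yearly visits; no section defines it so. No effect on test scores has been quantified. The primary caries outcomes are not affected.

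**What to change.** In section 7.2:

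- Define the exposed group as all children with signed consent in a participating school, from the consent date or the start of that school year, whether or not they were ever seen.
- Exclude every consenting child from the comparison pool.
- Start follow-up for each match on the same calendar date as for the exposed child.
- Name baseline absence as a required propensity covariate.
- Keep any comparison by receipt as a labelled sensitivity analysis.

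State one comparator, in the same terms, in sections 1.2, 2.2 and 7.2.

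The cost is wording only: consent records are already held, and sections 4.2.4 and 8.11 already provide for school rosters. The estimated effect may be somewhat diluted, because consented children who received no care count as exposed. Selection by consent is not removed and should be acknowledged as a limitation of this non-randomized comparison.
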